#### Implausible Values for Vital Signs and Solicited Adverse Events

The following numeric values will be considered implausible and will be excluded from summaries:

- Erythema: values less than 0 mm or equal to or greater than 500 mm
- Induration: values less than 0 mm or equal to or greater than 900 mm
- Temperature: values less than or equal to 33.0°C or equal to or greater than 42.0°C.

### **4.4 Analysis Sets**

#### **4.4.1 All Enrolled Set**

All subjects who signed an informed consent, underwent screening procedures, and have a subject number assigned.

#### **4.4.2 All Exposed Set**

All subjects in the All Enrolled Set who receive any study vaccination.

#### **4.4.3 Safety Sets**

Subjects will be analyzed as “treated” (i.e. according to the vaccine(s) a subject received, rather than the vaccine(s) to which the subject may have been randomized).

#### **Solicited Safety Set (solicited local and systemic adverse events and other solicited adverse events)**

- All subjects in the All Exposed Set with any solicited AE data.

#### **Unsolicited Safety Set (unsolicited adverse events)**

- All subjects in the All Exposed Set who attended at least 1 visit or had at least 1 safety call or at least 1 follow-up event (such as withdrawal from the study) after receiving any study vaccination.

#### **Overall Safety Set**

All subjects who are in the Solicited Safety Set and/or Unsolicited Safety Set.

#### **4.4.4 Full Analysis Sets (FASx), Immunogenicity**

FASx will be defined by visit and serogroup/B strain.

##### **Full Analysis Set 1**

- All subjects in the All Exposed Set who provided evaluable serum samples and whose assay results are available for at least 1 serogroup or B strain at Visit 4 for all study groups except the MenACWY group, or at Visit 2 for the MenACWY group.

##### **Full Analysis Set 2**

- All subjects in the All Exposed Set who provided evaluable serum samples and whose assay results are available for at least 1 serogroup or B strain at Visit 2 for all study groups except the MenACWY group.

##### **Full Analysis Set 3**

- All subjects in the All Exposed Set who provided evaluable serum samples and whose assay results are available for at least 1 serogroup or B strain at Visit 4 for all study groups except the MenACWY group, or at Visit 2 for the MenACWY group and at baseline for all study groups.

##### **Full Analysis Set 4**

- All subjects in the All Exposed Set who provided evaluable serum samples and whose assay results are available for at least 1 serogroup or B strain at Visit 2 and at baseline for all study groups except the MenACWY group.

#### **4.4.5 Per Protocol Set (PPSx), Immunogenicity**

PPS1, PPS2, PPS3, and PPS4 are the corresponding subsets of FAS1, FAS2, FAS3, and FAS4, respectively, who have no significant protocol deviations leading to exclusion from PPSx.

Protocol deviations are described in Section 5.2.

## **5 Subject Disposition**

### **5.1 Disposition**

Subject disposition will be summarized for the All Enrolled Set and for the Overall Safety Set, for each study group and overall. The summary will include the number of subjects in each analysis set defined in Section 4.4, the number and percentage of subjects who received any study vaccination, the number and percentage of subjects who were screen failures and major reason for screen

failure, the number and percentage of subjects who completed the study and the primary reason for withdrawal from the study.

Listings will be provided for disposition data based on the All Enrolled Set.

## 5.2 Significant Protocol Deviations

A significant protocol deviation is defined as a protocol deviation that is considered to have a significant impact on the immunogenicity results of the subject and will cause a subject to be excluded from PPSx. The number and percentage of subjects with each significant protocol deviation leading to exclusion from each PPSx will be presented and a listing of all significant protocol deviations leading to exclusion from PPSx will also be presented. Significant protocol deviations leading to exclusions from PPSx will be summarized by study group and overall for the All Enrolled Set.

All protocol deviations will be identified prior to the analysis and a clinical judgment will be necessary to classify each deviation as "significant" or "non-significant". A list of key significant deviations is provided below, but not limited to:

- Subjects enrolled who did not meet entry criteria including age at enrollment
- Subjects incorrectly vaccinated
- Subjects who did not receive study vaccinations as planned in protocol
- Subjects who did not have blood draws as planned in protocol
- Subjects with a blood draw outside of allowed time window
- Subjects with a vaccination done outside of allowed time window
- Subjects who incur a condition that has the capability of altering their immune response (i.e. human immunodeficiency virus or hematological malignancies) or are confirmed to have an alteration of their initial immune status.
- Subjects who receive any of the following during the study:
  - Any investigational or non-registered product (drug or vaccine) other than the study vaccine(s) used during the study period.
  - Immunosuppressants or other immune-modifying drugs administered chronically (i.e. more than 14 consecutive days in total) during the study period. Inhaled and topical steroids are allowed.

- Long-acting immune-modifying drugs administered at any time during the study period (e.g. infliximab).
- A vaccine not foreseen by the study protocol administered during the period of 14 days (for inactivated vaccines), 28 days (for live vaccines), or 7 days (for influenza vaccines) before or after administration of the study vaccine(s) at Visit 1 and Visit 3\*.  
\*In case an emergency mass vaccination for an unforeseen public health threat (e.g.: a pandemic) is organized by the public health authorities, outside the routine immunization program, the time period described above can be reduced if necessary for that vaccine provided it is licensed and used according to its SmPC and according to local governmental recommendations and provided a written approval of the sponsor is obtained.
- Drug and/or alcohol abuse that, in the opinion of the investigator, will interfere with the results of the study or pose additional risk to the subject.

These key significant deviations will be assessed based on the data collected in the electronic case report forms (eCRFs). The complete list of protocol deviations considered significant for this study will be reported in the Clinical Study Report (CSR). If a subject incurs a condition that has the capability of altering their immune response, this will be recorded as an AE and identified as a significant protocol deviation by medical monitoring.

## **6 Demographics and Baseline Characteristics**

Demographics and baseline characteristics will be summarized for the All Enrolled Set, All Exposed Set, Per Protocol Set 3, Full Analysis Set 3 and Overall Safety Set, presented by study group and overall. Subject demographic and baseline characteristics will also be presented in a listing for the All Enrolled Set.

### **6.1 Demographics**

The demographic characteristics consist of sex, race and center. The number and percentage of subjects by sex (Male, Female), race (American Indian or Alaska Native, Asian, Black or African American, Native Hawaiian or Other Pacific Islander, White, and Other) and center, will be reported.

### **6.2 Baseline Characteristics**

The baseline characteristics consist of age (years), age strata, baseline height (cm), baseline weight (kg), and baseline body mass index (BMI) (kg/m^2). Age is calculated as the number of days between the date of birth and the date of first

vaccination, converted to years. To ensure that the collection of date of birth will not jeopardize the privacy of personally identifiable information, only year of birth (YYYY) is collected on the eCRF. Date of birth will be imputed as 30JUNYYYY and Age will be calculated as (date of first vaccination – 30JUNYYYY)/365.25. BMI is calculated as (body weight in kilograms) / (height in meters).

Age (years), baseline height (cm), baseline weight (kg), and baseline BMI (kg/m^2) will be summarized using descriptive statistics. The number and percentage of subjects by age strata (10-17 years, 18-25 years), and by center and age strata will also be reported.

### **6.3 Medical History**

Medical history will be coded using the Medical Dictionary for Regulatory Activities (MedDRA) Version 20.1 or higher. The number and percentage of subjects with any medical history will be summarized overall and for each system organ class and preferred term by study group. Percentages will be calculated based on number of subjects in the All Enrolled Set by study group and overall.

Subject medical history data will also be presented in a listing.

### **6.4 Inclusion and Exclusion Criteria**

Subjects who did not meet inclusion criteria or met exclusion criteria will be presented in a listing for the All Enrolled Set. Inclusion and exclusion criteria are listed in the protocol sections 4.2 and 4.3.

## **7 Treatments and Medications**

### **7.1 Vaccination History and Concomitant Medications**

All vaccinations and medications will be coded according to the GSK Drug dictionary (GSKDrug) version 1.4 or higher.

#### **7.1.1 Vaccination History**

The number and percentage of subjects with any prior vaccinations recorded on the eCRF will be summarized by study group and overall, and the number and percentage of subjects who received each vaccination will be presented. Prior vaccinations will be displayed in a listing. All summaries will be performed using the All Enrolled Set.

#### **7.1.2 Concomitant Medications**

Concomitant medications are defined as any medications/products, except vitamins and dietary supplements, administered through 30 days post-vaccination.

A concomitant vaccination is defined as a vaccination administered in the period starting 28 days before the first dose of study vaccine(s) and ending at the last study visit (Day -28 to last study visit).

The number and percentage of subjects with at least one concomitant medication/vaccination will be summarized by study group and overall and the number and percentage of subjects taking each medication/receiving each vaccination will be presented by preferred term. Concomitant medications/vaccinations will be displayed in a listing. All summaries will be performed using the Overall Safety Set. Subjects with missing concomitant medication data will be handled as described in Section 4.3.

## 7.2 Extent of Exposure

Extent of exposure will be based on the All Enrolled Set and will be presented by study group and overall.

### 7.2.1 Compliance

The number and percentage of subjects who received any study vaccination will be presented, as well as the number and percentage of subjects who received all expected vaccinations during the study and the number and percentage of subjects who withdrew from study vaccine. A subject has withdrawn from study vaccine if

- For all study groups except MenACWY:
  - Vaccination was administered at Visit 1, no vaccination was administered at Visit 3 and the subject has data recorded for at least one of the following: Safety Call D75; Visit 4 or
  - Vaccination was not administered at Visit 1 and vaccination was not administered at Visit 3 and the subject has data recorded for at least one of the following: Safety Call D75; Visit 4.
- For MenACWY study group:
  - No vaccination was administered at Visit 1 and the subject has data recorded for at least one of the following: Safety Call D15; Visit 2.

In addition, the number and percentage of subjects who did not receive all vaccinations with reason (including subjects who received a partial vaccination) will be displayed by visit. The number of expected vaccinations for each study group can be found in Table 5.

**Table 5 Expected Number of Vaccinations**

Study Group	Expected Number of Vaccinations at Visit 1	Expected Number of Vaccinations at Visit 3*
-------------	--	---

MenABCWY	1	1
rMenBOMV + ACWY_S	2	2
rMenBOMV + ACWY_D	2	2
rMenBOMV	1	1
MenACWY	1	-

\* Subjects in the MenACWY group do not receive any vaccination at Visit 3.

### 7.2.2 Visit Attendance

The number and percentage of subjects who attended a visit or received a safety call within the interval described in Table 1 will be presented for the following visits:

- Visit 1
- Safety Call 1
- Visit 2
- Visit 3 (excluding the MenACWY group)
- Safety Call 2 (excluding the MenACWY group)
- Visit 4 (excluding the MenACWY group)

The number and percentage of subjects who received a 3 day pDiary reminder call and a 5 day pDiary reminder call after each visit, and if the subject/legal guardian was reached, will also be included.

Listings will be provided for the All Enrolled Set to provide details of visit attendance, safety calls, blood samples and pDiary reminder calls.

## 8 Immunogenicity Analysis

One of the main objectives of the study is to estimate the extent of a potential immune interference, due to immunological stress to lymph nodes in the arm where the combination vaccine is administered in comparison to injections in 2 different arms of individual vaccines. The sample size defines the conditions under which the observed reduction in immune response will be attributed to a true lymph-node effect or is the consequence of natural variability. An acceptable probability of falsely detecting the lymph-node effect was set to 10% (1-sided test). The minimum probability of detecting the lymph node effect is set to 80%.

Immune response will be measured using serum bactericidal assay using human complement (hSBA) testing performed on serum samples and titer results will be

analyzed for the immunogenicity analysis. Titers below LOD will be handled as described in Section 4.3.

The primary and secondary analysis will be based on PPSx. If the difference between PPSx and FASx is greater than 10%, a second analysis based on FASx will be performed to complement the PPSx analysis i.e. an analysis can be performed for PPS3 and FAS3, and for PPS4 only.

Titer results will be listed for the All Enrolled Set and the listing will indicate subjects included in each of PPSx and FASx. The listing will also indicate subjects with hSBA titers  $\geq$  LLOQ and subjects who experienced a 4-fold increase in hSBA titers since baseline.

For the remainder of Section 8 the Analysis Visit names defined in Table 4 will be used.

## 8.1 Summary and Analysis of hSBA Geometric Mean Titer

### 8.1.1 Primary Endpoint

Titer results are not normally distributed so summary statistics will be calculated using log-transformed titer results. The anti-logarithm of the summary statistics will be presented. Titer results will be summarized by study group, visit (Baseline, AVISIT 4) for each serogroup (A, C, W-135, Y) and the four individual serogroup B test strains. Titer results will also be summarized for the pooled serogroup B test strains. Missing titer results and results below the LOD will be handled as described in Section 4.3. Unadjusted and adjusted summaries will be calculated and will be displayed in the same output.

In addition, the distribution of antibody titers for each serogroup (A, C, W-135, Y) and the individual serogroup B test strains will be displayed using reverse cumulative distribution curves. The x-axis of the reverse cumulative distribution curves will be presented on a log scale. A reference line will be included to show LLOQ. All study groups for a single visit will be displayed on the same page, and visits will be displayed on separate pages.

Unadjusted summaries will include the number of subjects with non-missing titer results, geometric mean titer (GMT), geometric standard deviation (GSD), 80% confidence interval (CI) for GMT, minimum and maximum.

GMT will be calculated as the anti-logarithm of the mean of the log-transformed titer values i.e. anti-logarithm of  $\sum(\log_{10}(\text{titer}))/n$  where  $n$  is the number of subjects with non-missing titer results. GSD will be calculated as the anti-

logarithm of the standard deviation (SD) of the log-transformed data. The 80% CI for GMT will be calculated as the anti-logarithm of the endpoints of the 80% CI for the mean of the log-transformed data. The anti-logarithm is calculated as  $10^x$  where  $x$  is the statistic of interest calculated from the log-transformed data (e.g. mean, SD, 80% CI endpoints).

Adjusted summaries will be calculated using an analysis of covariance (ANCOVA) model. The adjusted GMT, standard error (SE) and 80% CI from the ANCOVA model will be presented.

Two ANCOVA models will be fitted, ANCOVA1 and ANCOVA2. ANCOVA1 will be used to estimate adjusted summaries for individual serogroups A, C, W-135, Y and the individual serogroup B test strains. ANCOVA2 will be fitted to the serogroup B data only to obtain adjusted summaries for the pooled serogroup B test strains.

ANCOVA1 for the immunogenicity analysis will be fitted in SAS using PROC MIXED. ANCOVA2 will be fitted using PROC MIXED with a REPEATED statement to account for within subject correlation. The TYPE =UN option will be used to specify an unstructured covariance model. The unstructured model was used to estimate sample study and does not make any assumptions about the form of the covariance structure in the data. The models will be fitted as follows:

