## 5.7.4. Biological samples evaluation

### 5.7.4.1. Immunological read-outs

**Table 8** Immunological read-outs

Blood sampling time point		No. subjects 	Component	Components priority rank 
Type of contact and time point	Sampling time point			
Visit 1 (Day 1)	Pre-Vacc 1	500	Serogroup B M14459 Serogroup B M07-0241084 Serogroup B 96217 Serogroup B NZ98/254 Serogroup C Serogroup Y Serogroup W-135 Serogroup A	1 2 3 4 5 6 7 8
Visit 2 (Day 31)	Post-Vacc 1	500	Serogroup B M14459 Serogroup B M07-0241084 Serogroup B 96217 Serogroup B NZ98/254 Serogroup C Serogroup Y Serogroup W-135 Serogroup A	1 2 3 4 5 6 7 8
Visit 4 (Day 91) 	Post-Vacc 2	400	Serogroup B M14459 Serogroup B M07-0241084 Serogroup B 96217 Serogroup B NZ98/254 Serogroup C Serogroup Y Serogroup W-135 Serogroup A	1 2 3 4 5 6 7 8

Approximate number of subjects.

Priority ranking for the serum bactericidal assay using human complement (hSBA) testing using the 8 indicator strains may be subject to change following the selection of the most appropriate hSBA format for each of the 8 serogroups. This will be documented in a protocol amendment or the clinical study report.

No blood collection and assays will be performed at this time point for the MenACWY treatment group.

Pre-Vacc: pre-vaccination; Post-Vacc: post-vaccination

In case of insufficient blood sample volume to perform assays for all antibodies, the samples will be analyzed according to priority ranking provided in [Table 8](#).

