### Titer Results

For a given subject and a given immunogenicity measurement, missing or non-evaluable measurements will not be replaced. Summaries and analyses for the pooled B serogroup strains will be performed using all available non-missing titer results. Subjects who have at least one non-missing titer result from the four possible serogroup B strains at a single visit will be included in the summaries and analyses for the pooled serogroup B strains.

Titer results recorded as below the LOD will be imputed with a numeric value of half the LOD for summaries and analyses and will be listed as reported in the raw data. For example, if an assay records a LOD of 80 and a sample is reported to have “< 80” as the titer level, a value of 40 will be used for the statistical summaries and analyses. Titer results recorded as “1:x” (where x is the dilution factor) will be assigned a numeric value of x. Titer results recorded as “>1:x” will be assigned a numeric value of x.

LOD and LLOQ values will be defined in the Clinical Study Report (CSR).

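### The unadjusted pooled-B GMT and its 80% CI are defined by a one-titer-per-subject formula, although up to four correlated titers per subject enter the summary

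*SAP*

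**What the plan says.** SAP 8.1.1 asks for unadjusted summaries by serogroup and by individual B strain, and adds: "Titer results will also be summarized for the pooled serogroup B test strains". One set of formulas serves all of these rows. In words, "GMT will be calculated as the anti-logarithm of the mean of the log-transformed titer values". In symbols, it is the sum of log10 titers over n, where n "is the number of subjects with non-missing titer results". The interval is the back-transform of the "endpoints of the 80% CI for the mean of the log-transformed data". No separate rule is given for the pooled row.

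SAP 4.3 (Titer Results) says what enters that row: "Summaries and analyses for the pooled B serogroup strains will be performed using all available non-missing titer results". It also sets the inclusion rule: "Subjects who have at least one non-missing titer result from the four possible serogroup B strains at a single visit will be included". A subject therefore brings between one and four titers.

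Within-subject correlation is handled in one place only: "ANCOVA2 will be fitted using PROC MIXED with a REPEATED statement to account for within subject correlation". That covers the adjusted pooled analysis. SAP 8.1.2 repeats the 8.1.1 analyses at AVISIT 2.

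**The concern.** The formula fits a summary with one titer per subject. For pooled B, the numerator runs over up to four titers per subject while the denominator counts subjects, so the two do not match. The SAP does not say whether the pooled n counts subjects or titers, whether titers are averaged within subject first, or how the unadjusted CI allows for correlation.

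A programmer has to repair this. Dividing by the number of titers is an obvious repair, given the SAP 4.3 wording. The ordinary CI would then treat about 400 values from 100 subjects as independent, although Protocol 10.4 itself says the strains are correlated.

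The pooled-B GMT is a listed primary endpoint, and adjusted and unadjusted values share one output. An unadjusted interval of the wrong width would sit beside a model-based one that does account for the correlation.

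**Working it through.** **Inputs from the documents.** Protocol 10.4: SD 0.435 (log10) for the average across the four B strains, 100 subjects per group, difference -0.130, one-sided alpha 0.10. SAP 8.1.1: 80% CI.

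**Inputs assumed.** The documents give no between-strain correlation (rho), single-strain SD or spread of strain means. I take rho from 0.2 to 0.8 and the SD of the four strain means (s_b) from 0 to 0.3 log10, with complete data.

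**Step 1: the plan's own figure.** The noncentrality is 0.130 / (0.435 × √(2/100)) = 2.113. The one-sided two-sample t-test with 198 df then has power 0.796, matching Table 14. So 0.435 is used as the SD of one averaged value per subject.

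**Step 2: dividing by subjects.** With four titers per subject, the sum over n is four times the mean log titer. Back-transformed, this is the GMT to the fourth power: an assumed GMT of 20 becomes 20⁴ = 160,000.

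**Step 3: dividing by titers, treated as independent.**

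- Single-strain variance implied by the planning SD: v = 4 × 0.435² / (1 + 3 rho) = 0.7569 / (1 + 3 rho)
- Naive SE = √((v + s_b²) / 400)
- Correct SE = 0.435 / √100 = 0.0435
- Coverage = 2Φ(1.2816 × naive SE / correct SE) − 1

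| rho | s_b | v | naive SE | naive / correct | coverage |
|---|---|---|---|---|---|
| 0.8 | 0 | 0.2226 | 0.0236 | 54% | 51% |
| 0.8 | 0.3 | 0.2226 | 0.0280 | 64% | 59% |
| 0.2 | 0 | 0.4731 | 0.0344 | 79% | 69% |
| 0.2 | 0.3 | 0.4731 | 0.0375 | 86% | 73% |

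Simulation (100 subjects, 8,000 runs) agrees. With equal strain means it gives 68.8%, 57.6% and 51.6% at rho 0.2, 0.5 and 0.8. With strain means 0.8, 1.0, 1.3 and 1.6 (SD about 0.30) it gives 73.1%, 64.7% and 59.3%.

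**Step 4: outside those ranges.** With equal means, coverage is 73.9% at rho 0.1 and 47.8% at rho 1.0. The naive SE equals the correct one when s_b² = 3 rho × v, that is, s_b = 0.53 at rho 0.2 and 0.73 at rho 0.8. Beyond that the interval is too wide: at rho 0.2 and s_b = √0.4731 = 0.69, coverage is 84.8%.

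**Step 5: averaging within subject first.** A t interval over subject means has simulated coverage of 79% to 81% for rho 0.1 to 0.8, with a mean half-width of 0.056 log10. With equal strain means, the naive half-width is 0.044 at rho 0.2 and 0.030 at rho 0.8. For an assumed GMT of 20, a half-width of 0.056 gives about 17.6 to 22.8, and 0.030 gives about 18.7 to 21.4.

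The GSD also changes meaning. It is 10^0.435 = 2.7 over subject means. Over single titers it is 10^0.55 = 3.5 at rho 0.5 with equal strain means (v = 0.7569 / 2.5, SD 0.55).

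**The case against.** **A third reading works.** If each subject contributes the average of their log titers, n as subjects is right and coverage is about 80%. This fits the planning SD in Protocol 10.4, and the SAP does not exclude it. The objection stands in that a correct analysis is open to the programmer. It does not remove the gap, because the SAP never states this step and SAP 4.3 speaks of using all available titers.

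**The fourth-power GMT.** A reader might infer that a figure such as 160,000 would be reported. The documents do not support that. The sentence before the formula calls for a mean, tables are independently double-programmed (SAP 4), and a pooled GMT far above every strain GMT would be noticed. The expression is faulty, but the realistic risk lies in the unstated repair.

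**The coverage range.** A reader might take 51% to 73% as a property of the plan. It is not: it rests on assumed values of rho and strain spread, and Step 4 shows results on both sides of it.

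**The lymph-node conclusion.** A reader might infer that the same-arm versus different-arms comparison is compromised. It is not. That comparison is a GMT ratio among the ANCOVA contrasts. SAP 8.1.1 assigns adjusted pooled B to ANCOVA2, with an unstructured within-subject covariance. No unadjusted between-group pooled ratio is specified, and Protocol 10.10 calls all analyses descriptive.

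**Drift toward some strains.** A reader might also infer that serum shortages would tilt the pooled mean toward higher-priority strains, since "In case of insufficient blood sample volume to perform assays for all antibodies, the samples will be analyzed according to priority ranking". Table 8 of Protocol 5.7.4.1 ranks the B strains 1 to 4 of 8, so the other serogroups are lost first. The documents give no rate of missing B results; this is a minor matter.

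**Conclusion.** The point holds as a specification fault in the descriptive unadjusted pooled-B rows at Baseline, AVISIT 4 and AVISIT 2. The stated formula does not give a mean when a subject has several titers, and the ordinary CI has the wrong width if those titers are treated as independent. The interval is usually too narrow: about 54% to 86% of the right width, with 51% to 73% coverage, for rho 0.2 to 0.8 and strain-mean SD 0 to 0.3 log10. Those figures also assume complete data, and that the planning SD of 0.435, estimated for the combination-vaccine arm of the previous study, applies. Greatly differing strain means can make it too wide.

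No decision rule depends on these rows. The individual-strain summaries, and the GMRs of SAP 8.2, which are not pooled, are unaffected. It should be corrected before programming because it concerns a listed primary endpoint and the correction is cheap.

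**What to change.** Add to SAP 8.1.1, for the unadjusted pooled-B summary: *For each subject and visit, the mean log10 titer over the available B strains is computed first. GMT, GSD and 80% CI are then computed over these subject means, with n equal to the number of subjects contributing.* SAP 8.1.2 inherits the rule at AVISIT 2.

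Keep the SAP 4.3 inclusion rule of at least one B titer, so that the adjusted and unadjusted rows draw on the same subjects. A footnote could give the number of subjects with fewer than four strains, since their means cover a different set of strains. If the row is instead limited to subjects with all four results, SAP 4.3 must be amended to match.

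The cost is one sentence and a small programming change. The unadjusted interval will usually be somewhat wider than one that treats the titers as independent. ANCOVA2 and its contrasts do not change.
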